5.0 Data and Safety Monitoring Plan

The study protocol will be reviewed and approved by the National Institutes of Health (NIH) before submission to individual center IRBs for approval. Participant enrollment may only begin with IRB approved consent forms.

Adverse events are to be collected and reported to the Study Chair following each completed study, or in the case of a laboratory abnormality, when the abnormal laboratory result is identified. The Study Chair will also review the study adverse event data after completed enrollment of the 8 healthy subjects and 8 subjects with UCD.

The study protocol will be reviewed and approved by the Data Safety and Monitoring Board (DSMB) of the Rare Disorders Clinical Research Consortium of the National Institutes of Health (NIH) before submission to individual center IRB's for approval. Participant enrollment may only begin with IRB approved consent forms.

This is an interventional pilot study that meets the federal definition of more than minimal risk.

5.1 Study Oversight

The Study Chair has primary oversight responsibility of this clinical trial. The NIH appointed Data Safety Monitoring Board (DSMB) has oversight responsibility of the Data Safety Monitoring Plan (DSMP) for this clinical trial. The DSMB will review accrual, patterns and frequencies of all adverse events, protocol compliance every 6 months. The DSMB makes recommendations to the NIH regarding the continuation status of the protocol.

Each site's Primary Investigator and their research team (co-Investigators, research nurses, clinical trial coordinators, and data managers) are responsible for identifying adverse events. Aggregate report- detailed by severity, attribution (expected or unexpected), and relationship to the study drug/study procedures – will be available from the DMCC for site review. Adverse events will be reviewed by the research team at the end of the study. A separate report detailing protocol compliance will also be available from the DMCC for site review on a monthly basis. The research team will then evaluate whether the protocol or informed consent document requires revision based on the reports.

5.2 Definitions and Standards

The Rare Diseases Clinical Research Network defines an adverse event as: "...an unfavorable and unintended sign, symptom or disease associated with a participant's participation in a Rare Diseases Clinical Research Network study."

Serious adverse events include those events that: "result in death; are life-threatening; require inpatient hospitalization or prolongation of existing hospitalization; create persistent or significant disability/incapacity, or a congenital anomaly/birth defects."

An unexpected adverse event is defined as any adverse experience...the specificity or severity of which is not consistent with the risks of information described in the protocol. Expected adverse events are those that are identified in the research protocol as having been previously associated with or having the potential to arise as a consequence of participation in the study

All reported adverse events will be classified using the Common Terminology Criteria for Adverse Events (CTCAE), developed and maintained by CTEP at National Cancer Institute.

5.3 Expected/Known Risks/Discomforts/Adverse Events

A definition of expected adverse events associated with study intervention and procedures are outlined below.

Study Drug/Intervention:

AHA:

Acetohydroxamic acid has been an FDA approved medication for the treatment of struvite nephrolithiasis for over 25 years. According to the prescribing information, about 150 patients, including children, have been treated, most for periods of more than 1 year.

Well controlled, long-term animal studies that identify the carcinogenic potential of AHA treatment have not been conducted. Acetamide, a metabolite of AHA, has been shown to cause hepatocellular carcinoma in rats at oral doses 1,500 times the human dose. AHA is cytotoxic and was positive for mutagenicity in the Ames test.

The pharmacokinetics of AHA in man are well known: 36-65% of the oral dose of AHA is excreted unchanged in the urine. The plasma half-life of AHA is approximately 5-10 hours in subjects with normal renal function.

According to the AHA (Lithostat) prescribing information, adverse reactions have occurred in up to thirty percent (30%) of the patients receiving AHA. In some instances, the reactions were symptomatic: in others, only changes in laboratory parameters were noted. Adverse reactions seem to be more prevalent in patients with pre-existing thrombophlebitis and/or in patients with advanced degrees of renal insufficiency.

The following reactions have been reported:

- 30% - Mild headaches during the first 48 hours of treatment, responsive to standard therapy
- Tremulousness and nervousness
- 20% - Gastrointestinal symptoms (nausea, vomiting, anorexia)
- 15% - laboratory findings characteristic of a hemolytic anemia
- Non-pruritic, macular rash on the upper extremities and face, usually concomitantly with alcoholic beverages, with spontaneous resolution
- Superficial phlebitis

Acute toxicity has not occurred. Milder overdoses resulting in hemolysis have occurred in an occasional patient with reduced renal function after several weeks or months of continuous treatment.

There is a small risk that the blood ammonia level will rise during the study. This unlikely possibility, would mostly likely result from toxicity of the AHA to the liver.

13C Urea:

Urea, and by extension, its stable isotope [¹³C]-urea, is a substance regarded by the FDA to be generally regarded as safe (GRAS). Administration of a small amount of stable isotopic urea should not pose a risk to subjects with urea cycle disorders, as the amount of ammonia generated by its hemolysis would represent only a small fraction of the total body ammonia.

There is a potential risk of contamination of the drug or isotope used in the study. However, a sterile and pyrogen-free preparation of the isotope is used, and the drug is manufactured via Current Good Manufacturing Practices (CGMP).

Study Procedures:

Venipuncture: The placement of the two Heplock intravenous catheters for blood sampling and [¹³C]-urea administration could result in a bruise or infection at the site of insertion. The vein in which the needle has been inserted to draw blood may become sore and red. A temporary “black and blue mark” may develop, and rarely fainting may occur. If a PICC line is inserted in the arm (by an interventional radiologist) intravenous sedation is given and involves risks of apnea or aspiration. There is also risk of vessel perforation and infection of the central line catheter.

There is a risk of loss of confidentiality, which could affect insurability and result in stigmatization.

5.4 Reporting Timeline

- Within **24 hours** (of learning of the event), investigators must report any reportable Serious Adverse Event (SAE) that:
 - Is considered life-threatening/disabling or results in death of subject
 - OR-
 - Is Unexpected/Unanticipated
- Investigators must report all other reportable SAEs within **5 working days** (of learning of the event).
- All other (suspected) reportable AEs must be reported to the RDCRN within **20 working days** of the notification of the event or of the site becoming aware of the event.

Local institutional reporting requirements to IRBs, any GCRC oversight committee and the FDA, if appropriate, remain the responsibility of the treating physician and the Study Chair.

5.5 RDCRN Adverse Event Data Management System (AEDAMS)

Upon entry of a serious adverse event, the DMCC created Adverse Event Data Management System (AEDAMS) will immediately notify the Study Chair, site PIs, the Medical Review Officer, and any additional agencies of any reported adverse events via email.

Serious adverse events: The NIH appointed Medical Review Officer (MRO) determines causality (definitely not related, probably not related, possibly related, probably related, definitely related) of the adverse event. The MRO may request further information if necessary and possibly request changes to the protocol or consent form as a consequence of the adverse event. A back-up notification system is in place so that any delays in review by the MRO beyond a specified period of time are forwarded to a secondary reviewer. The Adverse Event Data Management System (AEDAMS) maintains audit trails and stores data (and data updated) and communication related to any adverse event in the study.

Non-serious expected adverse events: Except those listed above as immediately reportable, non-serious expected adverse events that are reported to or observed by the investigator or a member of his research team will be submitted to the DMCC in a timely fashion (within 20 working days). The events will be presented in tabular form and given to the MRO and RDCRN DSMB on a bi-annual basis. Local site investigators are also required to fulfill all reporting requirements of their local institutions.

The DMCC will post aggregate reports of all adverse events (serious/not serious and expected, unexpected) for site investigators and IRBs.

5.6 Study Discontinuation

The NIH, RDCRN DSMB and local IRB's (at their local site) have the authority to stop or suspend this trial at any time. This study may be suspended or closed if:

- Accrual has been met
- The study objectives have been met
- The Study Chair / Study Investigators believe it is not safe for the study to continue
- The RDCRN DSMB suspends or closes the trial
- The NIH suspends or closes the trial
- The FDA suspends or closes the trial

5.7 Subject Discontinuation

An intent-to-treat approach will be used. All data acquired prior to termination for the reasons outlined below will be included in the primary analysis unless patient withdraws

consent. Every effort will be made to conduct a final study visit with the participant and participants will be followed clinically until, if applicable, all adverse events resolve.

- Withdrawal by the participant
- Withdrawal by the investigator
- Intercurrent illness or event that precludes further visits to the study site or ability to evaluate disease (e.g.-mental status change, large pleural effusion).

5.8 Data Quality and Monitoring Measures

As much as possible data quality is assessed at the data entry point using intelligent on-line data entry via visual basic designed screen forms. Data element constraints, whether independent range and/or format limitations or 'relative' referential integrity limitations, can be enforced by all methods employed for data input. QA reports assess data quality post-data entry. As we note, data quality begins with the design of the data collection forms and procedures and incorporates reasonable checks to minimize transcription and omission errors. Of the more important quality assurance measures are the internal validity checks for reasonableness and consistency.

- Data Monitoring: The RDCRN DMCC identifies missing or unclear data and generates a data query to the consortium administrator contact.
- Data Delinquency Tracking: The Data Management and Coordinating Center will monitor data delinquency on an ongoing basis.

6. Statistical Considerations

Linear longitudinal regression models will be developed to estimate the change in the time-averaged levels of blood $^{13}\text{CO}_2$ (primary endpoint), as well as blood levels of [^{13}C]-urea, ammonia and glutamine after AHA versus after non-AHA. When we evaluate the effect of AHA on each metabolite, the model will control for each metabolite's pretreatment level and will adjust variance estimates to account for the correlation between measurements on the same person as well as to take account of the random effect on the intercept. We will consider a relative AHA versus non-AHA difference in the time-averaged level of $^{13}\text{CO}_2$ of at least 20% as a signal that AHA can effectively reduce the impact of gut bacteria on urease activity. The presence of a clear effectiveness signal in healthy adults will be required before the crossover study can be implemented in adults with UCD.

Pilot data indicates that the expected level $^{13}\text{CO}_2$ in the absence of AHA treatment is 0.041% with a conservative precision of +/- 0.0075%. Therefore, using the sampsi procedure in Stata 12, a sample size of 8 crossover participants provides 90% power in 2-tailed testing at an alpha of 0.05 to detect a 20% relative (0.041% versus 0.033%)

difference in the time-averaged level of $^{13}\text{CO}_2$ on AHA versus non-AHA in either healthy or UCD affected adults.

7. Data Management

All study data will be collected via systems created in collaboration with the RDCRN Data Management and Coordinating Center and will comply with all applicable guidelines regarding patient confidentiality and data integrity. Data will be entered online, and submitted to the DMCC-managed UCDC RDCRN portal.

Blood and urine samples are to be collected on each study day and sent to the Children's Hospital of Philadelphia for stable-isotope analysis of $^{13}\text{CO}_2$ and ^{13}C -urea. As the number of enrollees is small, samples will be tracked via courier and email communication between CNMC and CHOP.

Samples may be kept for up to 3 years after the completion of the study, after which they will be discarded.

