1.1 Overview

This project will study the efficacy and safety of the pharmacologic blockade of urease in the nitrogen salvage pathway of intestinal microbes in subjects with partial urea cycle disorders. Additional trapping of ammonia as excretable urea may result in improved nitrogen excretion and reduced ammonia levels.

Urea cycle disorders (UCDs) are a group of disorders resulting from a complete or partial deficiency of one of the 6 enzymes or 2 transporters that comprise the urea cycle, the essential biochemical pathway which converts toxic ammonia into urea. These disorders have as a common feature, a reduced or complete inability to convert ammonia into urea, thereby resulting in high ammonia levels, or hyperammonemia. If untreated, hyperammonemia may result acutely in lethargy and coma, and chronically in intellectual disability. Current treatment for hyperammonemia is suboptimal, thus the search for new treatments is critical.

The urease inhibitor, acetohydroxamic acid (AHA, Lithostat®, Mission Pharmacal), is an FDA-approved product for another indication- the treatment of struvite nephrolithiasis in chronic urinary tract infections in both adults and children^{1,2}.

It is known that many urea-splitting bacteria also exist in the gut, and that in healthy individuals, approximately 15-30% of blood urea is degraded via gut bacteria into ammonia³, which returns to the liver via the portal vein, only to be recycled into urea. This percentage of degraded urea may even be greater in patients with urea cycle disorders, who are on a low protein-diet⁴ and whose gastrointestinal contents thus likely have lower nitrogen content, promoting bacterial recycling of nitrogen from available urea. Additionally, urea hydrolysis has been shown to be greatest in infants⁵, precisely the age at which hyperammonemic episodes are the most frequent in UCD patients.

We intend to study if AHA can inhibit gut bacteria degradation of urea, thereby reducing the quantity of ammonia returning to the liver. We intend to investigate this by studying subjects on two occasions at least 3 days apart:

On the first occasion, subjects will receive an intravenous dose of ¹³C-urea. Following the intravenous bolus of ¹³C-urea, over the subsequent 4 hours, we will collect several sequential measurements of blood and urine biomarkers from an IV catheter placed in the other arm. The intent is to obtain baseline ¹³CO₂ kinetics in the subject.

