On the second occasion, subjects will first receive an oral dose of AHA approximately 1 hour prior to the intravenous ¹³C-urea dose. Similar sequential measurements of blood and urine biomarkers will be performed. The intent is to observe a reduction in ¹³CO₂ when AHA is administered.

We intend to initially study a cohort of unaffected adult subjects. If successful, we will study adults with partial urea cycle disorders.

This study will be conducted in the Clinical Research Center (CRC) of the Clinical and Translational Research Institute (CTSI) of Children's National Medical Center (CNMC).

2. Specific Aims (Hypothesis and Objectives)

The specific aim is to investigate whether a single oral dose of AHA can inhibit intestinal bacterial urease in healthy subjects as well as in patients with partial UCDs, and whether it is safe. We propose a study with two components: the first without AHA, and the second after a single dose of AHA, 60mg/kg/d. We will evaluate whether AHA will inhibit bacterial urease, by measuring ^{13}C -labeled urea in blood and urine samples, following an intravenous load of ^{13}C -urea. Blood and urine ^{13}C -urea, plasma ammonia, plasma glutamine and blood urea will also be measured.

3. Background

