Enteral AHA has previously been administered to patients with hyperammonemia due to hepatic encephalopathy in two published reports^{6,7}. A single dose of oral 750 mg in adult patients was insufficient to result in any change in ammonia after 90 minutes in cirrhotic subjects free of *H. Pylori*⁷. However, in encephalopathy cirrhotic subjects administered AHA 20-60 mg/kg via naso-gastric tube, a statistically significant decreased in blood ammonia was observed⁶, with the effect most striking in subjects receiving a dose of 40-60 mg/kg/d.

This proposal would introduce a novel therapeutic approach for patients with UCD using a low-toxicity compound that may be particularly effective in patients with partial UCDs. There are two potential ways this approach may lower blood ammonia or excess nitrogen. The first is through blockage of new ammonia formation from urease. The second path may be increased consumption of residual dietary nitrogen by the gut flora in the absence of available nitrogen released through urease. Both effects may decrease the amount of nitrogen entering the portal vein. This new therapy will not interfere with other therapies, but would be complementary to them and may potentiate the nitrogen trapping effects of arginine and citrulline by preventing the degradation of the urea produced by their administration.

4. Study Design and Methods

This pilot crossover study will first evaluate the impact of AHA versus non-AHA primarily on ¹³CO₂ and secondarily on other biomarkers in healthy adults before applying the same crossover design to UCD subjects. A randomization table will determine if AHA or non-AHA will be performed first.

The figure below illustrates our study design:

Subjects will be required to fast for a minimum of 4 hours prior to beginning the study. Food consumption will not be permitted during the study; however subjects will be allowed to drink water or pedialyte throughout the study. Subjects will be observed and

various biomarkers will be collected throughout the 4-6 hours that they are studied. 5 mL of blood will be collected at each of the 7 time points shown above. Administration of [¹³C]-urea will be completed through an intravenous catheter. Blood draws will be done through the placement of a Heplock intravenous catheter on the opposite arm from where [¹³C]-urea was first administered. If there is not adequate vascular access, subjects will have a PICC (peripherally inserted central catheter) line placed instead.

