4.6 Schedule of Events

Subjects will be studied twice: once without and once with a single dose of acetohydroxamic acid, with the two study days at least 3-days apart.

Table 1. Laboratory investigations (each study day)

	Time point (min)							
	Baseline	0	30	60	90	120	180	240
Blood [¹³ C]-urea		X	X	X	X	X	X	X
Blood urea		X	X	X	X	X	X	X
Plasma glutamine		X	X	X	X	X	X	X
Ammonia		X	X	X	X	X	X	X
Blood ¹³ CO ₂		X	X	X	X	X	X	X
Urine [¹³ C]-urea		X						X
Urine urea		X						X
Safety labs:								
Hemoglobin	X							X
White blood count	X							X
Platelets	X							X
AST	X							X
ALT	X							X
Bilirubin	X							X
Creatinine	X							X

'Baseline' indicates at a time 0 on days when AHA is not administered or at a time prior to AHA administration on the days where AHA is administered. In addition, some of the blood and urine samples will be saved at the Clinical and Translational Science Institute at CNMC for up to 3 years after the conclusion of the study to test for the metabolism of AHA, after which the samples will be discarded.

5. Safety Monitoring

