10.1 Appendix

Drug Information:

Acetohydroxamic acid (Lithostat)

Pharmacology and Pharmaceutical Information:

Acetohydroxamic acid (AHA) is a stable, synthetic compound derived from hydroxylamine and ethyl acetate. It is a urease inhibitor that reversibly inhibits bacterial enzyme urease, thereby inhibiting the hydrolysis of urea and production of ammonia in urine infected with urea-splitting organisms. AHA is available for oral administration as 250 mg white, round tablets and manufactured by Mission Pharmacal. The intact drug is stored at controlled room temperature (20–25°C)

Treatment Information:

All subjects (healthy adults and UCD patients) will receive a single oral dose of 60 mg/kg acetohydroxamic acid during one of the treatment periods, based on the randomization assignment determining whether treatment occurs in the first or the second treatment cycle; doses will be rounded “up” or “down” to the nearest 250 mg to coincide with the available dosage form since the tablets cannot be scored. Patients will be instructed to fast for 4 hours prior to the study; subsequently, the ¹³C-Urea tracer will be administered 60 minutes after the ingestion of the acetohydroxamic acid dose.

¹³C-Urea

¹³C-Urea is a stable isotope produced by Cambridge Isotope Laboratories, Inc., Tewksbury, MA. The GMP grade pharmaceutical product is provided to Children’s National Medical Center as a sterile bulk powder.

Treatment Information:

All subjects (healthy adults and UCD patients) will receive a single IV infusion of ¹³C-Urea administered over 10-15 minutes, during both treatment cycles. The infusion will be prepared at a dose of 6 mg/kg and infused via a peripheral IV.

Preparation of ¹³C-Urea for Intravenous Use

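### On AHA days Table 1 takes no pre-AHA ammonia or glutamine sample, yet Section 6 adjusts both for a pretreatment level; adjusting for AHA-day time 0 would remove part of any effect already present

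*Combined protocol and SAP*

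**What the plan says.** Section 6 fits longitudinal models to 13CO2 (primary), [13C]-urea, ammonia and glutamine, comparing AHA with non-AHA, and adds that "the model will control for each metabolite's pretreatment level". It does not say which sample supplies that level.

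Table 1 (Section 4.6) applies to each study day. The ammonia and glutamine rows are blank under Baseline and marked at 0, 30, 60, 90, 120, 180 and 240 minutes. Only the safety labs are marked under Baseline. The footnote says that Baseline "indicates at a time 0 on days when AHA is not administered or at a time prior to AHA administration" on AHA days. Section 4 counts seven blood time points, which matches the columns from 0 to 240.

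On timing, Section 1.1 says "On the second occasion, subjects will first receive an oral dose of AHA approximately 1 hour prior to the intravenous" tracer dose, and the Appendix (10.1) says the "tracer will be administered 60 minutes after the ingestion of the acetohydroxamic acid dose". The Synopsis, under Primary Outcome Measures, refers to 2 hours after AHA without saying whether that runs to the tracer or to a measurement.

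On order, Section 1.1 puts the AHA day second, whereas Section 4 says "A randomization table will determine if AHA or non-AHA will be performed first" and the Appendix says treatment falls in a period "based on the randomization assignment determining whether treatment occurs in the first or the second treatment cycle".

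**The concern.** A pretreatment covariate is safe because treatment cannot have changed it. For ammonia and glutamine on AHA days, the schedule contains no such value. The only same-day candidate is time 0, which very probably follows AHA by about an hour. If AHA has begun to lower ammonia by then, adjusting for time 0 credits part of the drug effect to the starting level and understates the rest.

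At stake are two secondary outcomes. They matter to the rationale, because Section 1.1 presents reduced ammonia as the hoped-for benefit. An uncollected pre-AHA value cannot be recovered afterwards. The Synopsis lists the study as not yet enrolling, so the schedule can still be changed.

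**Working it through.** The plan gives no figure for ammonia or glutamine to reproduce; its sample-size statement concerns 13CO2 only.

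**1. Is AHA-day time 0 after AHA?** The footnote equates Baseline with time 0 on non-AHA days but moves it to before AHA on AHA days. That distinction is needed only if AHA-day time 0 is not itself pre-AHA. With the tracer 60 minutes after AHA (Section 1.1, Appendix) and time 0 as the start of the tracer curve, time 0 is very probably post-AHA. This is an inference: the design figure is not shown in the text available, and Table 1 does not define time 0.

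**2. Formula.** Let D be the mean AHA effect over the later samples, f the effect at time 0 divided by D, and b the covariate slope. The AHA-day covariate is shifted by f × D, so

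adjusted effect = D − b × f × D = D × (1 − b × f).

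The share lost is b × f. It is zero if f = 0.

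**3. Illustrative f.** Assume effect(t) = 1 − 2^(−(t − lag)/h), zero before the lag, with AHA 60 minutes before time 0 and later samples at 30, 60, 90, 120, 180 and 240 minutes. For lag 30 and h = 60 minutes:
- effect at time 0 = 1 − 2^(−30/60) = 0.293;
- later effects = 0.500, 0.646, 0.750, 0.823, 0.912, 0.956, mean 0.765;
- f = 0.293 / 0.765 = 0.38.

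| Assumed lag (min) | f at h = 30 / 60 / 120 min | Share lost at b = 0.5 |
|---|---|---|
| 0 | 0.78 / 0.60 / 0.47 | 39% / 30% / 24% |
| 30 | 0.54 / 0.38 / 0.29 | 27% / 19% / 15% |
| 60 or more | 0 | 0% |

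For b = 0.3 or 0.8, multiply the last column by 0.6 or 1.6. Lags, half-times and slopes are all assumptions.

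**4. Check by simulation.** Eight people, two conditions, six later samples, random-intercept model, f = 0.38, six assumed splits of person, day and residual variance. Mean fitted slopes were 0.27, 0.41, 0.50, 0.64, 0.75 and 0.88. Adjusting for AHA-day time 0 removed 11%, 15%, 19%, 24%, 28% and 33% of the effect, in line with b × f (for example 0.50 × 0.38 = 19%). Mean estimate over true effect was 0.996 to 1.003 with a pre-AHA covariate and 0.996 to 1.004 unadjusted. These runs hold f at 0.38, so they leave out the no-loss case.

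**5. Can the non-AHA day supply the covariate?** The study days are at least 3 days (72 h) apart and the stated half-life is 5 to 10 h. At least 72/10 = 7.2 half-lives therefore pass even if AHA comes first. Used as one value per person, non-AHA-day time 0 left the contrast essentially unbiased (0.99 to 1.04 of the true effect in a smaller simulation). It does not adjust for the AHA day's own starting level, and Section 6 does not specify it.

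**6. A pre-AHA sample needs a matching sample.** Pairing an AHA-day sample taken about 60 minutes before the tracer with a non-AHA-day sample at time 0 lets fasting drift enter the contrast. An assumed drift of 20% of the AHA effect over that hour biases the estimate by 0.20 × b: 10% at b = 0.5 and 16% at b = 0.8, up or down with the direction of drift.

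**The case against.** The strongest reply is that nothing in the plan says AHA-day time 0 will be the covariate. Pretreatment naturally means before treatment, and a sample an hour after AHA does not fit the word. Nor does the plan say that AHA changes ammonia within an hour. The only timed result it cites (Background) is no ammonia change 90 minutes after 750 mg in cirrhotic subjects. An unbiased contrast is available without any change to sampling, and these are unpowered secondary outcomes in an eight-person pilot.

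Most of that stands, and it is why the point is minor. A reader might infer that the planned analysis is biased. The documents do not support that: they show an adjustment whose covariate is undefined and, on AHA days, not collected. Bias follows only if time 0 is chosen and AHA has already acted.

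Two parts of the reply do not settle the matter. The 90-minute result came from a lower dose: 750 mg equals 60 mg/kg only at 750/60 = 12.5 kg body weight. The Background also reports lower ammonia at 20 to 60 mg/kg but gives no early time course, so no early effect cannot be assumed. And several candidate covariates, one of them open to bias, are a reason to name the choice before the data are seen.

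**Conclusion.** The point holds as a minor one, limited to ammonia and glutamine. Section 6 calls for a covariate that Table 1 does not collect on AHA days. Using AHA-day time 0 instead would shrink the AHA effect by b × f. The documents give neither b nor f, so the size is unknown: zero if AHA has not acted by time 0, and about 19% in the illustrative case of b = 0.5 and f = 0.38.

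Two stronger readings should be resisted. First, corner values of the assumed grid give much larger losses (for example 0.78 × 0.8 = 62%). These need immediate onset, a 30-minute half-time and a steep slope together, and nothing in the documents supports that combination. Second, a reader might extend the problem to the primary endpoint, because the adjustment sentence covers every metabolite. Time 0 comes at or before that day's tracer, so AHA has had no newly given label to act on. The 13CO2 comparison, the 20% signal that gates the UCD cohort, and [13C]-urea are not materially affected.

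The conclusion rests on time 0 being the tracer time, which is very probable but not stated. Blood urea has the same sampling gap, but Section 6 does not list it among the modelled outcomes.

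**What to change.** Choose one of the following before enrolment.

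**(a) Collect the covariate.** In Table 1, add ammonia and glutamine (and blood urea, if it will be modelled in the same way) to the Baseline draw already made before AHA. On non-AHA days, take a sample at the matching time before the tracer. Name these samples in Section 6 as the pretreatment level. Cost: one extra small tube per study day, at 5 mL taking 7 × 5 = 35 mL to 40 mL; an earlier draw on non-AHA days; and edits to Table 1, its footnote, Section 6 and the seven-time-point sentence in Section 4.

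**(b) Drop the adjustment.** State in Section 6, before analysis, that ammonia and glutamine are not adjusted for AHA-day time 0, and use the unadjusted within-person contrast, or only non-AHA-day time 0 as a person-level covariate. Cost: one sentence and no blood. The downside is precision when levels vary much from day to day. In the simulation with large day-to-day variance, the SD of the estimate as a share of the true effect was 0.27 to 0.37 unadjusted, against 0.17 to 0.24 with a pre-AHA covariate. With small day-to-day variance, (b) was as good or better (0.10 to 0.19 against 0.14 to 0.20).

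In either case, state in Table 1 what time 0 is, and reconcile the Synopsis's 2 hours with the 60 minutes in Section 1.1 and the Appendix. The fixed order in Section 1.1 and the randomized order in Section 4 and the Appendix should also be reconciled, because the order decides whether non-AHA-day samples precede AHA for everyone.
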